12.2 Analysis Sets

The **All Subjects Set** will include all subjects who were randomized or received at least 1 dose of study drug. This analysis set will be used for all individual subject data listings and the disposition summary table, unless otherwise specified.

The **Full Analysis Set (FAS)** will include all randomized subjects who were *F508del* homozygous and received at least 1 dose of study drug. The FAS will be used for all efficacy analyses.

The **Safety Set** will include all subjects who received at least 1 dose of study drug. The Safety Set will be used for all safety analyses.

12.3 Statistical Analysis

This section presents a summary of the planned statistical analyses of efficacy and safety. Analysis details will be provided in the SAP.

12.3.1 General Considerations

Continuous variables will be summarized using the following descriptive summary statistics: the number of subjects (n), mean, standard deviation (SD), standard error (SE), median, minimum value (min), and maximum value (max). The precision of the measurement for each continuous variable will be specified in the SAP. Unless otherwise specified, minimum and maximum values will be reported with the same precision as the units of the raw data. The mean and median will be reported to 1 additional decimal place, and the SD and SE will be reported to 2 additional decimal places. Any values that require a transformation to standard units (metric or International System [SI]) will be converted with the appropriate precision.

Categorical variables will be summarized using counts and percentages. Percentages will be presented to 1 decimal place.

Baseline value, unless otherwise specified, will be defined as the most recent non-missing measurement (scheduled or unscheduled) collected before the first dose of study drug. For ECG, the baseline will be defined as the average of the most recent triplicate pretreatment measurements before the first dose of study drug.

Change (absolute change) from baseline will be calculated as postbaseline value – baseline value.

Relative change from baseline will be calculated as (postbaseline value – baseline value)/baseline value.

The treatment-emergent (TE) period will include the time from the first dose to the Safety Follow-up Visit or 28 days after the last dose of the study drug for subjects who did not complete the Safety Follow-up Visit.

Rules for handling missing data will be described in the SAP.

12.3.2 Background Characteristics

12.3.2.1 Subject Disposition

The number and percentage of subjects in each disposition category (e.g., randomized, dosed, included in the FAS, included in the Safety Set, completed Treatment Period, completed study/Safety Follow-up Visit, and discontinued treatment or study with a breakdown of the reasons for discontinuation for treatment or study, respectively) will be summarized overall and by treatment group.

12.3.2.2 Demographics and Baseline Characteristics

Demographic, background (e.g., medical history), and baseline characteristics will be summarized using descriptive summary statistics. Protocol deviations/violations will be provided in an individual subject data listings.

The following demographics and baseline characteristics will be summarized overall and by treatment group for the FAS and will include (but are not limited to): sex, race, age, baseline weight, baseline height, baseline body mass index (BMI), baseline ppFEV₁, baseline whole lung mucus clearance through 60 minutes, and baseline small bowel AUC over 1-minute mean pH increments through 30 minutes after gastric emptying.

No statistical tests will be carried out to evaluate any baseline imbalance between treatment groups.

12.3.2.3 Prior and Concomitant Medications

Medications used in this study will be coded using the World Health Organization Drug Dictionary Enhanced and categorized as the following:

- Prior medication: any medication that started before initial dosing of study drug, regardless of when it ended
- Concomitant medication: medication continued or newly received during the TE period
- Post-treatment medication: medication continued or newly received after the TE period

A given medication may be classified as a prior medication, a concomitant medication, or a post-treatment medication; both prior and concomitant; both concomitant and post-treatment; or prior, concomitant, and post-treatment. If a medication has a missing or partially missing start/end date or time and if it cannot be determined whether it was taken before the first dose of study drug, concomitantly during the TE period, or after the TE period, it will be considered in all 3 categories of prior, concomitant, and post-treatment medication.

Prior medications and concomitant medications will be summarized descriptively based on the FAS. Post-treatment medications will be provided separately in an individual subject data listing.

12.3.2.4 Study Drug Exposure and Compliance

Exposure to study drug will be summarized for the FAS in terms of duration of treatment a subject received (in days), defined as the last day minus the first day of study drug plus 1.

Dosing compliance will be summarized for the FAS, and will be derived as $100 \times [(\text{total number of pills dispensed}) - (\text{total number of pills returned})] / (\text{total number of pills planned to be taken per day} \times \text{duration of study drug exposure in days})$.

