^y Study drug will be administered as described in [Section 10.2](#). On Day 1 through the morning of the Day 29 Clinic Visit, study drug will be administered within 30 minutes of starting a meal with fat-containing food such as a “standard CF” high-fat, high-calorie meal or snack. At the Day 29 Visit, subjects will receive a snack bar in place of the morning meal. On days of scheduled visits, the morning dose of study drug will be administered at the site after the last predose assessment has been completed.

^z Study drug count will occur at the Safety Follow-up Visit for all subjects who discontinue the study and for whom the Safety Follow-up Visit replaces the ETT.

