10.2 Administration

Study drug tablets will be administered orally during the Treatment Period as shown in Table 10-1.

Table 10-1 Study Drug Administration - Treatment Period

Treatment Arm	Time	Drug(s) and Dose(s) Administered Route of Administration
VX-661/IVA	AM	100-mg VX-661 / 150-mg IVA FDC tablet, oral
	PM	150-mg IVA tablet, oral
Placebo	AM	VX-661/IVA-matching placebo FDC tablet, oral
	PM	IVA-matching placebo tablet, oral

AM: morning; FDC: fixed dose combination; IVA: ivacaftor; PM: evening.

Study drug should be administered within 30 minutes of starting a meal with fat-containing food such as a “standard CF” high-fat, high-calorie meal or snack according to the following guidelines:

1. Throughout the Treatment Period, study drugs will be administered after the start and before the end of a meal. It is recommended that the duration of each meal associated with study drug intake (i.e., breakfast and dinner/snack, as applicable) should not exceed 30 minutes.
2. Study drug should be administered q12h (\pm 2 hours). For each subject, all doses (morning and evening) of study drugs will be taken at approximately the same time each day. For example, the morning dose could be taken at 08:00 every morning and the evening dose could be taken at 20:00 every evening throughout the study.
3. On days of WMC administration, subjects will fast overnight and will ingest a snack bar provided at the site in place of the morning high-fat meal immediately before ingesting the WMC. Subjects will fast for 4 hours after the capsule is taken and snack bar is consumed.

4. At the Day 1 Visit, all subjects will be observed for 6 hours after the morning dose of the study drug.
5. The date, amount taken, and time of study drug administration, including whether food was taken with each dose, will be recorded for 2 days before PK sample collection and on the days of PK sample collection.
6. On days of scheduled visits, the morning dose of study drug will be administered at the site after predose assessments have been completed. The meal or snack will be provided by the site for the morning dose of study drug.
7. If a subject's scheduled visit is to occur in the afternoon, the following guidelines must be used:
 - If the dose in the clinic will be within 6 hours of the subject's scheduled morning dose, the subject should withhold their morning dose of study drug and the morning dose will be administered in the clinic.

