10.4 Missed Doses

If a subject misses a dose and recalls the missed dose within 6 hours, the subject should take his/her dose with food. If more than 6 hours have elapsed after his/her usual dosing time, the subject should skip that dose and resume his/her normal schedule for the following dose. For example,

- If the morning dose of study drug should have been taken at approximately 08:00, and the subject remembers at 12:00 that he/she forgot to take that dose, he/she should take the dose with food as soon as possible.
- If the morning dose of study drug should have been taken at approximately 08:00, and more than 6 hours have elapsed beyond the scheduled dosing time (i.e., the time is past 14:00), the subject would resume dosing with the evening dose at approximately 20:00.

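### The compliance formula pools the morning VX-661/IVA tablet with the evening IVA tablet and counts one evening tablet not due, so it does not identify VX-661 adherence and full adherence scores 98.3%

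*Protocol*

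**What the plan says.** Section 12.3.2.4 gives one compliance percentage per subject: "Dosing compliance will be summarized for the FAS, and will be derived as" 100 times a ratio of tablet counts. The numerator is "total number of pills dispensed" less the total returned. The denominator is "total number of pills planned to be taken per day" multiplied by the duration of exposure, which is "defined as the last day minus the first day of study drug plus 1". Nothing separates one kind of tablet from the other.

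Table 10-1 in Section 10.2 gives two different tablets a day in the active arm. The morning one is the "100-mg VX-661 / 150-mg IVA FDC tablet, oral"; the evening one is ivacaftor only. The placebo arm has two matching tablets.

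On when dosing ends, footnote y to Table 3-2 reads: "On Day 1 through the morning of the Day 29 Clinic Visit, study drug will be administered" close to the start of a fat-containing meal. On timing within a day, Section 10.4 has a subject skip a dose that is more than 6 hours late; for a skipped morning dose its example is that "the subject would resume dosing with the evening dose at approximately 20:00".

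**The concern.** The study asks what the combination does over about four weeks, and a reader facing a weak result will look to the compliance table to see whether VX-661 was taken. All the VX-661 is in the morning tablet, and a morning dose that is skipped under Section 10.4 loses that day's VX-661 entirely. The formula gives it the same weight as a missed evening ivacaftor tablet, so the reported percentage cannot answer the question.

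Separately, the exposure definition counts the last day as a whole day and the formula multiplies it by two tablets. If the last scheduled dose is a morning dose, one planned tablet in the denominator was never due, and no subject on that schedule can reach 100% by following instructions.

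**Working it through.** The protocol states a formula but no compliance figure, so there is nothing to reproduce. The check applies the formula to defined patterns of intake.

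**Inputs**
- Tablets per day: 1 morning + 1 evening = 2 (Table 10-1).
- Treatment length: 29 ± 3 days, so 26 to 32 (synopsis; Section 8.1.2).
- Exposure days: D = last day − first day + 1 (Section 12.3.2.4).
- Last scheduled dose: morning of Day 29 (Table 3-2, footnote y).
- Assumption: every tablet not taken is returned, so dispensed minus returned equals taken.

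**Full adherence, last dose in the morning of day D**

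Tablets due and taken: D morning + (D − 1) evening = 2D − 1. Denominator: 2D. Score: 100 × (2D − 1)/(2D).

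| D | Taken | Denominator | Score |
|---|---|---|---|
| 26 | 51 | 52 | 98.1% |
| 29 | 57 | 58 | 98.3% |
| 32 | 63 | 64 | 98.4% |

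The shortfall is always one tablet, 1.6 to 1.9 points. If an evening dose is also given on Day 29, the score is 58/58 = 100%.

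**Pooling, D = 29, last dose in the morning**

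| Pattern | Pooled score | VX-661 tablets taken | Evening tablets taken |
|---|---|---|---|
| 7 morning missed | 50/58 = 86.2% | 22/29 = 75.9% | 28/28 = 100% |
| 7 evening missed | 50/58 = 86.2% | 29/29 = 100% | 21/28 = 75.0% |
| 11 morning missed | 46/58 = 79.3% | 18/29 = 62.1% | 28/28 = 100% |
| 11 evening missed | 46/58 = 79.3% | 29/29 = 100% | 17/28 = 60.7% |
| All morning missed | 28/58 = 48.3% | 0/29 = 0% | 28/28 = 100% |
| All evening missed | 29/58 = 50.0% | 29/29 = 100% | 0/28 = 0% |

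A pooled 79.3% is thus compatible with VX-661 intake anywhere from 62.1% to 100%. At the extreme, subjects with none and all of their VX-661 differ by 1.7 points on the pooled scale.

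**Does correcting the denominator alone suffice?** No. With 57 doses due, seven missed tablets score 50/57 = 87.7% whichever tablet was missed. The two faults need separate corrections.

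**After both corrections**, full adherence at D = 29 gives 29/29 = 100% for the morning tablet and 28/28 = 100% for the evening tablet, and seven missed morning tablets show as 75.9% and 100%.

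**The case against.** **Little depends on the figure.** Compliance is descriptive. The protocol sets no numerical compliance threshold, defines no per-protocol set in Section 12.2, and uses compliance in none of the key analyses in Section 12.4.1. The one-tablet shortfall applies by the same rule in both arms. All of this stands and keeps the point minor.

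**Other data bear on VX-661 intake.** Predose VX-661 and M1-661 concentrations are taken on Days 28 and 29 (Section 11.3.1), and dosing is recorded on those days and the two days before (Section 10.2, item 5). This partly stands: it covers exposure near the endpoint visits but not the preceding weeks. Table 10-2 lists the products separately, so a tabulation by tablet may still be possible. The pooled percentage fails to identify VX-661 adherence; it does not follow that the trial's data could not.

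**The shortfall is not universal.** Under the afternoon-visit rule in Section 10.2, item 7, an evening dose can be the clinic dose, giving 58/58. That is a real exception, though it fits Day 29 poorly: the motility capsule is given that day with the morning dose and a snack bar, after an 8-hour fast. Footnote y is also mainly about meals, and it implies the last dose rather than declaring it.

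**The SAP may refine this.** Section 12.3 calls itself a summary. But the formula is written out in full, so the criticism is of a stated rule rather than of an omission.

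**Two stronger readings are not supported.** A reader might infer that summarising compliance on the FAS distorts adherence. It does not: the choice of set decides which subjects are tabulated and changes no subject's percentage, and the efficacy set is a defensible choice for compliance. Section 12.2 says "The Safety Set will be used for all safety analyses", so exposure and adverse-event tables could differ in denominator by any dosed subject later found not homozygous, but Section 12.3.2.1 reports the size of both sets.

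A reader might also infer that interruptions required by Section 11.7.8 will commonly look like poor adherence. The formula would count withheld days if a subject later resumed. However, after Day 1 Table 3-2 schedules chemistry only at Day 29, early termination and Safety Follow-up, so an interruption with resumption inside the period would need unscheduled tests or a late-reported Day 1 result. If drug is stopped for good, exposure ends at the last dose and later days never enter the denominator.

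**Conclusion.** The point holds, as a minor one. The single percentage in Section 12.3.2.4 does not identify VX-661 adherence: seven missed morning tablets over 29 days score 86.2% against 75.9% of VX-661 taken. On the standard schedule it also understates full adherence by one tablet, giving 98.3% at 29 days and 98.1% to 98.4% over the permitted range.

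This rests on a last dose in the morning and on untaken tablets being returned. The missed-dose patterns are illustrations of what the formula allows; the documents give no reason to expect morning doses to be missed selectively. No endpoint estimate, test or safety conclusion changes.

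**What to change.** Replace the single formula in Section 12.3.2.4 with two, one for the morning fixed-dose tablet and one for the evening ivacaftor tablet, each applied to the matching placebo in the control arm:

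100 × (tablets of that type dispensed − returned) / (doses of that type due from first to last dose).

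Count no evening dose as due on the last day unless one was scheduled under the afternoon-visit rule. On the standard 29-day schedule the denominators are then 29 and 28. A combined figure, if still wanted, should use their sum, 57.

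The cost is a wording change in the protocol or SAP, a few lines of programming, and making sure that sites record returns by tablet type. No visit, assessment or endpoint changes.

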12.4 Efficacy Analysis

12.4.1 Analysis of Key Efficacy Variables

The variables for key efficacy endpoints are:

- Absolute change in ppFEV₁ from baseline at Day 28,
- Absolute change in average percent whole lung clearance through 60 minutes from baseline at Day 28,
- Absolute change in small bowel AUC over 1-minute mean pH increments through 30 minutes after gastric emptying from baseline at Day 29,
- Absolute change in sweat chloride from baseline at Day 29, and

The analysis for each of these endpoints will be performed for the VX-661/IVA combination group based on a 2-sided paired-*t* test performed at $\alpha = 0.05$ to test a null hypothesis of a zero mean change from baseline, using the Day 28 or Day 29 changes from baseline. The results from these analyses will include the observed mean change from baseline, a 95% CI, and a 2-sided *P* value. A sensitivity analysis based on the Wilcoxon signed rank test will be described in the SAP.

A descriptive analysis that includes the observed mean change from baseline at Day 28 or Day 29 and 95% CI will also be presented for the placebo group.

Further, a descriptive analysis of observed values and change from baseline values at each scheduled time point will be presented by treatment group.

A large black rectangular redaction box covers the majority of the page content, starting below the header and ending above the footer. It is positioned in the center of the page and spans most of its width.

12.4.3 Safety Analysis

All safety analyses will be based on the set of data associated with the TE period for subjects in the Safety Set.

The overall safety profile of study drug will be assessed based on the following safety and tolerability endpoints:

- Treatment-emergent adverse events (TEAEs)
- Clinical laboratory values (i.e., hematology, serum chemistry, vitamin levels, lipid panel, coagulation, and urinalysis)
- ECGs
- Vital signs
- Pulse oximetry

All safety data will be presented in individual subject data listings.

12.4.3.1 Adverse Events

For analysis purposes, AEs will be classified as pretreatment AEs, TEAEs, or post-treatment AEs, defined as follows:

- Pretreatment AE: any AE that started before the first dose of study drug
- TEAE: any AE that increased in severity or that was newly developed at or after the first dose of study drug through the end of the TE period
- Post-treatment AE: any AE that increased in severity or that was newly developed beyond the TE period

For AEs with missing or partial start dates, if there is no clear evidence that the AEs started before or after study drug treatment, then the AEs will be classified as TEAEs.

AE summary tables will be presented for TEAEs only, overall and by treatment group, and will include the following:

- All TEAEs
- TEAEs by strongest relationship
- TEAEs by maximum severity
- TEAEs leading to treatment discontinuation
- Serious TEAEs
- TEAEs leading to death
- Frequently reported TEAEs

Summaries will be presented by MedDRA system organ class and preferred term using frequency counts and percentages (i.e., number and percentage of subjects with an event). When summarizing the number and percentage of subjects with an event, subjects with multiple occurrences of the same AE or a continuing AE will be counted once, only the maximum severity level will be presented in the severity summaries, and the strongest relationship level in the relationship summaries. In addition, a listing containing individual subject level AE data for all deaths and other serious and significant AEs will be provided separately. All AEs, including pre- and post-treatment AEs, will be presented in individual subject data listings.

12.4.3.2 Clinical Laboratory Assessments

For the treatment-emergent laboratory measurements, the observed values and change from baseline values of the continuous hematology and chemistry results will be summarized in SI units overall and by treatment group at each scheduled time point.

The number and percentage of subjects with at least 1 potentially clinically significant (PCS) event during the TE period will be summarized overall and by treatment group. The PCS (postbaseline) shift from baseline will also be summarized for selected laboratory parameters. The PCS criteria and the parameter selection criteria will be provided in the SAP.

Results of urinalysis and the serum pregnancy test will be listed in individual subject data listings only. In addition, a listing containing individual subject hematology, chemistry, and coagulation values outside the reference ranges will be provided. This listing will include data from scheduled and unscheduled time points.

12.4.3.3 Electrocardiogram

For the treatment-emergent ECG measurements, a summary of observed values and change from baseline values will be provided overall and by treatment group at each scheduled time point for the following ECG measurements: RR, PR, QT, and QT corrected for HR intervals (QTcF), QRS duration, and HR.

The number and percentage of subjects with at least 1 PCS event during the TE period will be summarized overall and by treatment group. The PCS (postbaseline) shift from baseline will also be summarized. The PCS criteria will be provided in the SAP.

Additional ECG analyses will be described in the SAP.

12.4.3.4 Vital Signs

For the treatment-emergent vital signs measurements, the observed values and change from baseline values will be summarized overall and by treatment group at each scheduled time point.

The following vital signs parameters will be summarized: systolic and diastolic blood pressure (mm Hg), body temperature (°C), HR (beats per minute), and respiratory rate (breaths per minute).

The number and percentage of subjects with at least 1 PCS event during the TE period will be summarized overall and by treatment group. The PCS (postbaseline) shift from baseline will also be summarized. The PCS criteria will be provided in the SAP.

Additional vital sign analyses will be described in the SAP.

12.4.3.5 Pulse Oximetry

For the treatment-emergent pulse oximetry measurements, a summary of observed values and change from baseline values will be provided overall and by treatment group at each scheduled time point for the percent of oxygen saturation by pulse oximetry.

The number and percentage of subjects with shift changes from baseline (normal/missing and low according to the reference range) to the lowest percent of oxygen saturation during the TE period will be summarized overall and by treatment group.

